1    **Official Title**

2    **Influenza Vaccination Effectiveness of a Quadrivalent Inactivated Vaccine in**  
3    **Pregnant Women and Young Infants (Aged 6 months and Below) During**  
4    **Influenza Season 2019-2020**

5

6    **Unique Protocol ID: 16708**

7    **6 May 2021**

8

9

10

11

12

13

14

15

16

17

18

19

20 **Statistical analysis**

21 Women were excluded from the statistical analysis for the following reasons that  
22 occurred before the onset of influenza season: decision to withdraw from the study,  
23 loss to follow-up, post-partum influenza vaccination (cocooning), pregnancy  
24 discontinuation, spontaneous abortion, perinatal death. Women were followed for the  
25 entire influenza season, regardless of onset of influenza or ILI. The analysis was  
26 restricted to the influenza season. The primary outcome of the study was influenza  
27 onset in pregnant women. Secondary outcomes were the onset of influenza in their  
28 infants and the onset of ILI, ARI, febrile episode, pneumonia, healthcare seeking,  
29 hospitalization, use antibiotics and use of antivirals in pregnant women and their  
30 infants. Categorical and continuous variables were compared between vaccinated and  
31 unvaccinated groups using the  $\chi^2$  test and T-test, respectively. Logistic regression  
32 analysis was conducted in order to identify factors significantly associated with a  
33 history of influenza vaccination in 2019-2020. Odds ratio (OR) and confidence  
34 intervals (CIs) were estimated. We have used a Bayesian model selection for logistic  
35 regression models with random intercept. The primary outcome of interest was to  
36 estimate the average rate of influenza for each group (vaccinated versus unvaccinated  
37 group). Our data was a 2 by 2 cross-tabulated data arising from two binary variables  
38 with possible values 0 or 1. The first variable was whether a pregnant woman has  
39 been vaccinated (value =1) or not (value =0). The second variable was the age group  
40 of the pregnant woman. The first group consisted of pregnant women aged less than  
41 32 years (value =0) or not (value=1). We compared the vaccinated pregnant women  
42 group with the group of non-vaccinated pregnant women to model the proportion of  
43 effectiveness that is the event that a pregnant woman had influenza. We used the  
44 Bayesian beta-binomial model due to data heterogeneity because of a large number of

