45 zeros were observed. Given this heterogeneity assumption, a Bayesian hierarchical  
46 random-effects model was used to analyze the data. The assumption of our model  
47 was that the number of individuals  $y_j$  responding to influenza vaccination is  
48 binomially distributed as:

49  $y_j \sim \text{Binomial}(p_j, n_j)$ ,

50 where the success rate ( $p_j$ ) was the probability of influenza onset in mothers and  $n_j$   
51 was the number of individuals in the  $j$ th group. We note that there are only 2 groups  
52 ( $j=1,2$ ): the vaccinated and the not vaccinated groups. The probability ( $p_j$ ) itself  
53 follows a beta distribution with parameters ( $a_j, b_j$ ). Non-informative distributions  
54 priors distributions were placed on the parameters of the beta distributions. P-values  
55 of 0.05 or less were considered statistically significant. IVE against influenza was  
56 estimated as follows:  $[1 - (\text{incidence rate of influenza in vaccinated women} / \text{incidence rate of influenza in unvaccinated women})] \times 100$  [11]. The statistical analysis was  
57 conducted using R 3.6 (R Foundation for Statistical Computing).  
58

59

60

61 **Results**

62 A total of 949 pregnant women were enrolled in the study (Figure 1). Of them, 94  
63 women were excluded from the analysis because of the following reasons: lost to  
64 follow-up or decision to withdraw from the study (65 women), post-partum influenza  
65 vaccination (cocooning) (25 women), spontaneous abortion (3 women), and perinatal  
66 death (1 woman). Therefore, 855 pregnant women were included in the analysis.  
67 Their mean age was 32.9 years (range: 18-45 years) and their mean gestational age at  
68 enrollment was 23.3 weeks (range: 3-39 weeks).

69 Of the 855 pregnant women, 525 (61.4%) were vaccinated against influenza and 330  
70 (38.6%) refused vaccination. No serious adverse event occurred. Pregnant women  
71 with a history of influenza vaccination the past (2018-2019) season were more likely  
72 to get vaccinated against influenza in 2019-2020 compared to women with no history  
73 of vaccination (91.8% versus 55.1%, p-value<0.001). In the logistic regression  
74 analysis the following variables were significantly associated with a history of  
75 influenza vaccination in 2019-2020: lower gestational age (OR: 0.998; CI: 0.998-  
76 0.999), influenza vaccination the past season (OR: 8.8; CI: 4.7-16.2), and no smoking  

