77 during pregnancy (OR: 0.6; CI: 0.4-0.9).

78 ***Estimation of IVE in pregnant women***

79 Of the 855 pregnant women included in the analysis, 636 women were still pregnant  
80 during the 2019-2020 influenza season and comprised the study group for the  
81 estimation of IVE in pregnancy. Of them, 406 women (63.8%) were vaccinated  
82 against influenza and 230 (36.2%) refused vaccination. Table 1 shows their  
83 characteristics by influenza vaccination status.

84 Twelve of the 636 pregnant women tested positive for influenza (8 cases of influenza  
85 A/H3N2, 2 cases of A/H1N1 and 2 cases of influenza B). Table 2 summarizes their  
86 morbidity by influenza vaccination status. The incidence of influenza differed  
87 between vaccinated women (6/406; 1.47%) and unvaccinated women (6/230; 2.6%),  
88 however the difference was not statistically significant. Similarly, higher rates of  
89 febrile episode, ILI, pneumonia, healthcare seeking, hospitalization, use of antibiotics  
90 and antivirals were noted in the unvaccinated group compared to the vaccinated  
91 group, however none of these differences reached statistical significance (Table 2).  
92 The IVE of QIV against influenza was 43.5% for pregnant women during 2019-2020  
93 in Greece. The IVE of QIV against influenza was 43.5% (95% CI: 28.4%-55.6%) for  
94 pregnant women during 2019-2020 in Greece.

95 According to the regression model the age was not a predictor of influenza onset in  
96 the sample of pregnant women. Influenza vaccination of pregnant women reduced  
97 their logit to develop influenza by -4.2 (95% CI -3,7 -4,7), which indicates that  
98 influenza vaccination added a statistically significant protection to pregnant women.

99 ***Estimation of IVE in infants***

100 A total of 474 infants were born before or during the 2019-2020 influenza season and  
101 constituted the group for the estimation of IVE in infants. Their mean birth weight  
102 was 3189 g (range: 630-4650 g) and their mean gestational age was 39.1 weeks  
103 (range: 28-42 weeks). There were 281 (59.3%) infants whose mothers were  
104 vaccinated during pregnancy and 193 (40.7%) infants of unvaccinated mothers. The  
105 unvaccinated mothers had a mean gestational age of 31.2 weeks at enrollment  
106 compared to a mean gestational age of 28.3 weeks of vaccinated mothers (p-value

107 <0.001); no other significant difference was noted between the two groups (data not  
108 shown).

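### The SAP's claim of statistically significant protection against influenza contradicts its own tests; both IVEs are crude, and their printed intervals are about four times too narrow on the log scale.

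*SAP*

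**What the plan says.** **Estimator.** The Statistical analysis section defines IVE as one minus a ratio whose numerator is the "incidence rate of influenza in vaccinated women" and whose denominator is the same quantity in unvaccinated women. There is no covariate term. The beta-binomial model has two groups, vaccinated and not. The one other variable named is maternal age, cut at 32 years: "The second variable was the age group". The section also says "We have used a Bayesian model selection for logistic" regression models with a random intercept, without listing the candidate covariates. The significance threshold is 0.05.

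**Comparator.** Under Results, the unvaccinated women are those who declined the vaccine (330 of 855; 230 of the 636 analysed for IVE in pregnancy).

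**Women.** Of the influenza incidences the text says "however the difference was not statistically significant" (Table 2, p=0.314). The same subsection prints an IVE of 43.5% (95% CI 28.4% to 55.6%). It then says that vaccination reduced "their logit to develop influenza by -4.2 (95% CI -3,7 -4,7), which indicates that" "influenza vaccination added a statistically significant protection to pregnant women".

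**Infants.** Table 3 gives p=0.59 for influenza, and the text limits significance to ARI and antiviral use. The printed IVE is 31.4% (4% to 51%). A logit reduction of -4.2 (-3.6, -4.9) is again read as significant protection.

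**Imbalances.** Table 1 shows differences in past-season vaccination (23.2% vs 6.1%, p<0.001), gestational age (19.3 vs 21.6 weeks, p=0.003) and smoking (6.9% vs 16.0%, p=0.001). For the infant cohort, unvaccinated mothers averaged 31.2 weeks at enrollment, "compared to a mean gestational age of 28.3 weeks of vaccinated mothers" (p<0.001).

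**The concern.** Each subsection gives two incompatible answers to one question. The test finds no significant difference in influenza, while the regression sentence and the IVE interval imply a clear one. A reader who takes the closing sentence and the interval leaves with demonstrated protection of mothers and infants, on 12 and 8 cases.

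The comparison is also between women who accepted and women who refused vaccination, and they differ on factors that the document itself records. None of these factors is reported in an influenza analysis. The logistic regression that does name past vaccination, gestational age and smoking models vaccine uptake, not influenza. The IVEs are nevertheless presented without being called unadjusted.

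**Working it through.** **Inputs.** Women: 6/406 vaccinated, 6/230 unvaccinated (Table 2). Infants: 4/281 and 4/193 (Table 3).

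**1. Reproduce the point estimates.** IVE = 1 - (a/n1)/(b/n0).
- Women: 1 - (6/406)/(6/230) = 1 - 0.567 = 43.3%. Rounded rates give 1 - 1.47/2.6 = 43.5%, as printed.
- Infants: 1 - (4/281)/(4/193) = 1 - 0.687 = 31.3%. Rounded rates give 1 - 1.42/2.07 = 31.4%, as printed.

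Both are therefore crude, and the small differences are rounding.

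**2. Reproduce the tests.** Uncorrected Pearson chi-square is 1.014 (p=0.314) for women and 0.290 (p=0.590) for infants, as printed.

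**3. IVE intervals.** SE(log RR) = sqrt(1/a - 1/n1 + 1/b - 1/n0).

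| | SE from counts | 95% CI from counts | Printed CI | SE implied by printed CI | Ratio of SEs |
|---|---|---|---|---|---|
| Women | 0.571 | -74% to 82% | 28.4% to 55.6% | 0.122 | 4.7 |
| Infants | 0.701 | -171% to 83% | 4% to 51% | 0.172 | 4.1 |

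The implied SE is [ln(1 - lower) - ln(1 - upper)]/3.92. A two-group beta-binomial posterior, the model the SAP names, agrees with the counts: with Beta(1,1) priors about -67% to 81% in women and -153% to 81% in infants. Beta(0.5,0.5) and Beta(0.01,0.01) give wider intervals.

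**4. The logit of -4.2.**
- Women: ln(6/400) = -4.20 vaccinated, ln(6/224) = -3.62 unvaccinated; contrast -0.58 (95% CI -1.72 to 0.56).
- Infants: ln(4/277) = -4.24, ln(4/189) = -3.86; contrast -0.38 (-1.78 to 1.02).
- If -4.2 were the contrast, the odds ratio would be exp(-4.2) = 0.015. Expected vaccinated-group cases would be about 406 × 0.00040 = 0.16 women and 281 × 0.00032 = 0.09 infants, against 6 and 4 observed.
- The value is close to the vaccinated group's own logit, but the intervals are not. The counts give -5.01 to -3.39 and -5.22 to -3.25 for that logit; the document prints -4.7 to -3.7 and -4.9 to -3.6.

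**5. How far confounding could move the IVE (illustration; all risk ratios assumed, factors taken as independent).** The bias factor is

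B = [(0.232·RRp + 0.768)/(0.061·RRp + 0.939)] × [(0.069·RRs + 0.931)/(0.16·RRs + 0.84)] × RRg^(-d), and IVE = 1 - RR/B,

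where p is past vaccination, s is smoking, and g is gestational age per SD. The standardised difference d is back-calculated from the p-values: 0.246 in women; at least 0.31 in infants, because only p<0.001 is given.
- Women, RRp 0.5 to 2 and RRs 1 to 3: 27.9% to 51.2%. RRp=2 with RRs=3 gives 43.4%, essentially no shift.
- Adding RRg of 1.5 or 0.67: 20.4% to 55.8%.
- Infants, gestational age alone: 22.1% to 39.4% at d=0.31, which is a minimum width; about 16% to 44% at d=0.5.

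All of these ranges lie well inside the sampling intervals in step 3.

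**The case against.** **Confounding is unproven.** The document gives no link between any imbalanced factor and influenza, and the illustrative shifts rest on assumed risk ratios. This stands. A reader might infer that the IVEs are biased in a known direction or by a material amount. The documents do not support that.

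**The covariates may have been considered.** The Bayesian model selection lists no candidates, so one cannot say that past vaccination, smoking or gestational age were never tried. What can be said is that none is reported in an influenza analysis.

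**Twelve and eight events cannot carry a multi-covariate model.** This stands too, and it is why adjustment is not a required correction. Nor would adjustment have a predictable result. In a logistic model with past vaccination as the only covariate (normal priors: SD 10 for the intercept, 2.5 for vaccine and for past vaccination), suppose 6 vaccinated and 2 refusing cases had been vaccinated the season before. The standardised IVE is then about 72% (11% to 91%). That split is extreme, but the printed data allow it. It would thus be wrong to assert that every adjusted interval includes zero.

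**The source of -4.2 is not established.** It is tempting to say that the vaccinated group's logit was misread as a vaccine effect. The point values fit, but the printed intervals do not, so the source is unresolved. That -4.2 is not the contrast does not depend on this explanation.

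None of these objections touches the main contradiction, which sits within single subsections and needs no adjustment to show.

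**Conclusion.** The concern holds in this form. The two protection conclusions are contradicted by the document's own p-values of 0.314 and 0.59. The logit of -4.2 cannot be a vaccine contrast, since the counts give -0.58 and -0.38 with intervals that include zero. The printed IVE intervals are about four times too narrow on the log scale; the counts support 43.3% (-74% to 82%) in women and 31.3% (-171% to 83%) in infants. These results use only the printed counts and large-sample log-scale intervals, and the beta-binomial check leads to the same conclusion.

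Both IVEs are unadjusted comparisons of acceptors and refusers with documented imbalances. They support an imprecise association, not a causal or significant effect. Equally, a non-significant result with limits of 82% and 83% is no evidence that the vaccine fails to protect.

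**What to change.** 1. Replace both protection sentences with wording that agrees with the tests. For women, for example: *Influenza was less frequent in vaccinated women (6/406 vs 6/230); the unadjusted difference was not statistically significant (p=0.314).* Do likewise for infants (4/281 vs 4/193, p=0.59).
2. Withdraw -4.2 as a vaccine effect in both subsections. Report the vaccinated-minus-unvaccinated log odds contrast with its interval: from the counts, -0.58 (-1.72 to 0.56) and -0.38 (-1.78 to 1.02).
3. Replace both printed IVE intervals with ones recomputed from the counts, about -74% to 82% and -171% to 83%. Otherwise the new wording would stand beside intervals that exclude zero.
4. Label both IVEs as unadjusted comparisons of women who accepted and women who refused vaccination.

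Optional only: an adjusted estimate beside each crude one, labelled post hoc and exploratory, with a statement that at 12 and 8 events it depends on single cases and on the prior.

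**Cost.** Items 1 to 4 are text changes and a short recalculation from counts already printed. The real cost is that the stated conclusions become less favourable.

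### The hierarchical beta-binomial model has only the two exposure groups as units, so its random-effects layer does no work, and it defines no vaccine contrast to support the claims of significant protection

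*SAP*

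**What the plan says.** All of the model description is in the SAP's Statistical analysis section.

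- **Reason for the model.** It is a "Bayesian beta-binomial model due to data heterogeneity because of a large number of" zeros; the next sentence fragment reads "zeros were observed. Given this heterogeneity assumption, a Bayesian hierarchical", followed by the random-effects label.
- **Units.** y_j is binomial with probability p_j and size n_j, and p_j is defined as the mothers' probability of influenza onset. On the index j: "We note that there are only 2 groups", namely vaccinated and not vaccinated.
- **Second level.** p_j "follows a beta distribution with parameters" (a_j, b_j), so each group has its own pair. Non-informative "priors distributions were placed on the parameters of the beta distributions"; no family or scale is given.
- **Target.** The aim is to "estimate the average rate of influenza for each group (vaccinated versus unvaccinated" group). IVE is defined separately, as one minus the ratio of incidence rates.
- **Other elements.** The section also names logistic "regression models with random intercept. The primary outcome of interest was to" (the target just quoted), a 2 by 2 layout of vaccination and age group, and a p-value threshold of 0.05.

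Under Results, IVE is 43.5% for mothers and 31.4% for infants. In both populations the regression model is said to show that vaccination reduced the logit of influenza by -4.2, and this is read as significant protection.

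**The concern.** A random-effects layer is useful when there are several exchangeable units whose spread can be estimated. Here the only units are the two arms of the comparison, with one count each, and a_j and b_j carry the group index. Two counts face four hyperparameters. Nothing is shared between groups and no between-unit variance can be estimated.

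The stated reason does not rescue the choice. With one yes/no outcome per woman, over-dispersion cannot be seen, and a large share of zeros is what a low incidence produces.

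The model also stops at group rates. It contains no parameter for the effect of vaccination and no Bayesian rule for declaring one, and it leaves open whether the average rate means p_j or the beta mean a_j/(a_j+b_j). Yet the Results report a model-based vaccine effect and call it significant, while Table 2 gives p = 0.314 and Table 3 gives p = 0.59 for the same counts. What is at stake is the trial's headline claim of protection.

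**Working it through.** **Inputs.** Tables 2 and 3: mothers 6/406 vaccinated and 6/230 unvaccinated; infants 4/281 and 4/193. The hyperpriors below are assumptions, because the SAP names none.

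**1. The SAP's own point estimates.**
- Mothers: 1 − (6/406)/(6/230) = 1 − 230/406 = 43.35%. From the printed 1.47% and 2.6%: 1 − 1.47/2.6 = 43.46%. The stated 43.5% is the crude ratio, up to rounding.
- Infants: 1 − 193/281 = 31.3%, against the stated 31.4%.
- The uncorrected chi-square gives p = 0.314 and p = 0.59, as in the tables.

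**2. The zeros.** A plain binomial at 12/636 predicts 636 × (1 − 12/636) = 624 event-free women. That is the observed number. It is an identity, and it shows that the count of zeros carries no information on heterogeneity.

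**3. What the hyperprior does and does not move.** The SAP's model was fitted to the mothers' counts, independently per group, under nine vague hyperpriors: a, b ~ U(0,10), U(0,100), U(0,1000), Gamma(1, 0.01), Gamma(0.1, 0.1), log-uniform(0.01, 100), log-uniform(0.001, 1000), half-Cauchy(1), and uniform mean with (a+b)^(-0.5) uniform.

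| Quantity (range over the nine) | From p_j | From a_j/(a_j+b_j) |
|---|---|---|
| Median, vaccinated | 1.4% to 1.7% | 1.8% to 13.7% |
| Median, unvaccinated | 2.5% to 2.9% | 3.0% to 14.5% |
| IVE, median | 43% to 44% | 7% to 41% |
| IVE, lower 95% limit | -81% to -66% | -4042% to -115% |
| Pr(IVE > 0) | 0.84 to 0.85 | 0.52 to 0.80 |

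The p_j are identified by the counts. The beta means are not.

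**4. The reported -4.2.**
- Mothers: logit(6/406) = ln(6/400) = -4.20; logit(6/230) = ln(6/224) = -3.62. The difference is the log odds ratio, -0.58 (SE 0.58).
- Infants: ln(4/277) = -4.24; ln(4/189) = -3.86. The difference is -0.38 (SE 0.71).
- A true logit reduction of 4.2 would be an odds ratio of exp(-4.2) = 0.015, which cannot stand beside an IVE of 43.5% or 31.4%.

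In both populations -4.2 agrees with the level in the vaccinated group. A level that differs from zero on the logit scale only says that influenza was rare among the vaccinated.

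**5. A direct contrast.** With independent p_j ~ Beta(0.5, 0.5), the posteriors are Beta(6.5, 400.5) and Beta(6.5, 224.5) for mothers, and Beta(4.5, 277.5) and Beta(4.5, 189.5) for infants. Simulated IVE = 100 × (1 − p_vaccinated/p_unvaccinated):

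| | Median | 95% credible interval | Pr(IVE > 0) |
|---|---|---|---|
| Mothers | 43% | -75% to 82% | 0.84 |
| Infants | 31% | -174% to 83% | 0.71 |

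Beta(1, 1) for mothers gives 43% (-67% to 81%, Pr 0.85). The log-risk-ratio Wald interval for mothers is -74% to 82%. All include no effect.

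**The case against.** The strongest reply is that the layer is harmless. p_j is the SAP's own probability of influenza onset, integrating out a_j and b_j merely leaves a vague prior on each p_j, and the IVE from p_j stays at 43% to 44%. This stands, and it rules out four stronger readings that a reader might infer.

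- **That the hyperprior, not the data, sets the vaccine effect.** This is true only of a_j/(a_j+b_j). The SAP never names that quantity and does not compute IVE from it. The reported 43.5% is the crude ratio.
- **That a random intercept on the two groups shrinks the contrast.** The SAP does not state the unit of the random intercept. The Results report a coefficient for vaccination, which points to a regression term instead.
- **That the posterior is improper.** This would hold for unbounded flat hyperpriors, which the SAP does not specify.
- **That the model was picked after seeing the zeros.** The whole document is in the past tense. That shows retrospective drafting, not when this model was chosen.

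It is also fair to say that the 0.05 rule has a proper place: the chi-square tests, t-tests and logistic regressions produce p-values. The gap is narrower, in that the Bayesian model has no criterion of its own.

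The reply does not cover the false rationale, the missing contrast, or the use of a group-level logit as a vaccine effect.

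**Conclusion.** The model as written should be replaced. Its hierarchical layer is redundant and its hyperparameters are barely identified, although the primary point estimate is not distorted by it. The material defect is that the model yields group rates only, while the Results draw an effect claim from it. The -4.2 is numerically the vaccinated group's own logit; the contrasts are -0.58 and -0.38, each no larger than about one standard error. How the -4.2 was actually obtained cannot be told from the document, and only its point value is matched here.

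On a stated contrast, the posterior intervals run from -75% to 82% for mothers and from -174% to 83% for infants, so neither statement of significant protection is supported. This rests on the counts in Tables 2 and 3 and on Beta(0.5, 0.5) priors; for mothers, the lower limit is -81% to -66% over the nine vague hyperpriors.

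The narrow reported IVE interval for mothers (28.4% to 55.6%) is not explained by this model either. It implies a standard error of (ln 0.716 − ln 0.444)/3.92 = 0.122 for the log risk ratio, against 0.571 from the counts. That is a separate reporting error, not a consequence of the hyperprior.

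**What to change.** 1. Delete the hierarchical layer and the zeros rationale. State independent p_j with a named fixed prior, for example Beta(0.5, 0.5), with Beta(1, 1) as sensitivity analysis. Say that the average rate means p_j.
2. Define the target as 100 × (1 − p_vaccinated/p_unvaccinated), for mothers and for infants. Report its posterior median, 95% credible interval and Pr(IVE > 0).
3. Base any claim of protection from the Bayesian model on that contrast, for example the 95% interval excluding 0. Keep the 0.05 p-value rule for the chi-square, t-test and logistic analyses.
4. Reconcile the two-group model with the random-intercept logistic model and the vaccination-by-age layout. If age is kept, enter vaccination and age as fixed terms and report the vaccination coefficient as the contrast.
5. Withdraw or correct the -4.2 statements and the conclusions of significant protection in both Results subsections on IVE.

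The cost is SAP wording and a few lines of code, with no new data. The point estimates barely change, but the conclusion becomes less favourable.

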109 Overall, 8 of the 474 infants tested positive for influenza (5 cases of influenza  
110 A/H3N2, 2 cases of influenza A/H1N1 and 1 of influenza B). Table 3 summarizes  
111 their morbidity by maternal influenza vaccination status. Infants of unvaccinated  
112 mothers more often developed influenza, febrile episodes, ILI, ARI, AOM and  
113 pneumonia and had increased rates of healthcare seeking, hospitalization, use of  
114 antibiotics and use of antiviral agents compared to infants whose mothers were  
115 vaccinated, however these differences reached statistical significance only for ARI  
116 and use of antiviral agents (p-values=0.012 and 0.036, respectively). The IVE against  
117 influenza for infants was estimated at 31.4% in 2019-2020. The IVE against influenza  
118 for infants was estimated at 31.4% (95% CI: 4%-51%) in 2019-2020.

119 According to the regression model the age of pregnant women was not a predictor of  
120 influenza onset in the sample of young infants. Additionally the influenza vaccination  
121 of pregnant women reduced the logit of their infants to develop influenza by -4.2  
122 (95% CI -3.6, -4.9), which indicates that influenza vaccination during pregnancy  
123 added a statistically significant protection to young infants.

124

125

126

127

128

129 **Table 1. Characteristics of pregnant women (n=636) by influenza vaccination status**130 **Characteristic** **Vaccinated** **Unvaccinated** **P-value**131 **n=406 (%)** **n=230 (%)**

132 \_\_\_\_\_

133 Mean age, years (range) 33.1 (21-45) 32.3 (18-45) 0.055

134 Mean gestational age, weeks (range) 19.3 (3-39) 21.6 (3-39) 0.003

135 Underlying disease 49 (12.2) 32 (14.0) 0.512

136 Influenza vaccination the past season 94 (23.2) 14 (6.1) <0.001

137 Mean no. of cohabitants (range) 1.7 (0-8) 1.8 (0-8) 0.147

138 Children <5 years 161 (39.8) 79 (34.5) 0.190

139 Mean no. of children <5 years (range) 0.5 (0-3) 0.4 (0-3) 0.325

140 No smoking during pregnancy 350 (93.1) 173 (84.0) 0.001

141 142 Smoking during pregnancy 26 (6.9) 33 (16.0)

143 \_\_\_\_\_

144

145

146

147

148

149

150

151 **Table 2. Morbidity (%) of pregnant women (n=636) by influenza vaccination status**

152	Type of morbidity	Vaccinated	Unvaccinated	P-value
153		n = 406 (%)	n = 230 (%)	
154	Influenza*	6 (1.5)	6 (2.6)	0.314
155	Febrile episode	17 (4.2)	13 (5.7)	0.402
156	ARI	115 (28.3)	50 (21.7)	0.069
157	ILI	11 (2.7)	11 (4.8)	0.169
158	Pneumonia	2 (0.5)	4 (1.7)	0.118

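### Each of 18 secondary comparisons is judged at an unadjusted 0.05, and two infant results are called significant although the primary chi-square comparison is not (p=0.314)

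*SAP*

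**What the plan says.** - **Primary outcome.** SAP, Statistical analysis, names a single one, influenza in pregnant women: "restricted to the influenza season. The primary outcome of the study was influenza".
- **Secondary outcomes.** The same section lists influenza in infants, then eight outcomes for both women and infants: "infants and the onset of ILI, ARI, febrile episode, pneumonia, healthcare seeking", continuing "hospitalization, use antibiotics and use of antivirals in pregnant women and their". That makes 1 + 8 × 2 = 17 comparisons.
- **Test and threshold.** Categorical outcomes are compared by chi-square. The only significance rule is that p-values "of 0.05 or less were considered statistically significant. IVE against influenza was". No adjustment, hierarchy or exploratory label accompanies it.
- **What was tested.** Table 2 gives p-values for the primary outcome and 8 secondary maternal rows. Table 3 gives p-values for 10 infant rows. One of these is acute otitis media, which is not on the SAP's list but appears in the text on infants: "mothers more often developed influenza, febrile episodes, ILI, ARI, AOM and".
- **What was claimed.** No maternal difference is called significant. For infants the text reads "vaccinated, however these differences reached statistical significance only for ARI", then "and use of antiviral agents (p-values=0.012 and 0.036, respectively). The IVE against".

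**The concern.** One threshold serves the primary outcome and 18 secondary rows alike, so the overall chance of a false secondary claim is not controlled. The primary chi-square comparison did not reach the threshold, and nothing in the SAP says what a secondary result then means. Two infant outcomes are nevertheless reported in the language of a formal test. A reader may take lower ARI and lower antiviral use in infants of vaccinated mothers as established findings, although one of them rests on three events.

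**Working it through.** **Inputs** (Tables 2 and 3)

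| Comparison | Vaccinated | Unvaccinated | Printed p |
|---|---|---|---|
| Influenza, women (primary) | 6/406 | 6/230 | 0.314 |
| ARI, infants | 17/281 | 27/193 | 0.012 |
| Antivirals, infants | 0/281 | 3/193 | 0.036 |

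**Step 1. Reproduce the printed p-values.** Uncorrected Pearson chi-square on 1 df, X² = N(ad − bc)² / (product of the four margins), two-sided by construction.

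- Primary: 636 × (6×224 − 400×6)² / (406×230×12×624) = 1.01, p = 0.314. Reproduced.
- Antivirals: 474 × (0×190 − 281×3)² / (281×193×3×471) = 4.40, p = 0.036. Reproduced. The smallest expected count is 3×193/474 = 1.22. Fisher's exact test gives 0.067, which is the chance that all three events fall in the unvaccinated group: (193×192×191)/(474×473×472).
- ARI: 474 × (17×166 − 264×27)² / (281×193×44×430) = 8.57, p = 0.0034. Not reproduced. The likelihood-ratio (0.0038), Yates (0.0057) and Fisher (0.0056) versions do not give 0.012 either.

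Of the 19 p-values in the two tables, 16 reproduce to within 0.001. Besides infant ARI, the exceptions are infant healthcare seeking (0.144 printed, 0.071 from counts) and infant hospitalization (0.277 printed, 0.227 from counts). Neither crosses 0.05. These mismatches are a separate reporting error.

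**Step 2. Count the tests.** 8 maternal + 10 infant = 18 secondary rows: the 17 listed plus AOM.

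**Step 3. Chance of false positives if all nulls are true and the tests are independent.**

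- At least one among 18: 1 − 0.95¹⁸ = 0.603. For the 17 listed: 0.582.
- At least two among 18: 0.226. Expected number: 18 × 0.05 = 0.9.
- Allowing for sparse rows: three rows have one event in total and cannot reach 0.05. Using each row's actual test size at its observed event total gives 0.52 for 18 rows and 0.35 for the 10 infant rows, still under independence.

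**Step 4. Adjust the two claims.** ARI is the smallest p-value, so Bonferroni and Holm both multiply it by m. Antivirals come second, so Holm multiplies by m − 1.

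| Result | p used | 10 infant rows | All 18 rows |
|---|---|---|---|
| ARI, printed | 0.012 | 0.12 | 0.216 |
| ARI, from counts | 0.0034 | 0.034 | 0.062 |
| Antivirals, Bonferroni | 0.036 | 0.36 | 0.648 |
| Antivirals, Holm | 0.036 | 0.324 | 0.612 |

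The one surviving entry is ARI from its counts, within the infant rows. It depends on the uncorrected chi-square: with Fisher's 0.0056 the value across 10 rows is 0.056.

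**Step 5. The estimate behind ARI.** Risk ratio (17/281)/(27/193) = 0.0605/0.1399 = 0.43. SE of the log = √(1/17 − 1/281 + 1/27 − 1/193) = 0.295, so the unadjusted 95% CI is 0.24 to 0.77.

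**The case against.** The best case against the point is that this is a non-randomised cohort with one named primary outcome, secondary outcomes labelled as such, and every p-value printed, including those that are not significant. Whether to adjust secondary outcomes in such a study is a matter of convention, and the SAP gives no basis for choosing between 10 and 18 rows. This stands against a compulsory adjustment. It does not stand against labelling: the SAP sets a significance rule with no distinction between primary and secondary outcomes and then uses it to make claims.

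It can also be said that the SAP's conclusion about infants (statistically significant protection) comes from the regression model, not from the two table rows. That is correct, and a multiplicity rule would not touch it. The same holds for the model-based claim of significant protection in women, which sits beside p=0.314. Both are separate matters. The point here is confined to the sentence on ARI and antivirals.

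Several stronger readings are tempting, and the document does not support them:

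- *A reader might infer that all 18 comparisons are declared significant.* All 18 are judged at 0.05; two are declared significant.
- *That 60% is the actual error rate.* It assumes independence and an exact 5% size in every row. Sparse rows already lower it to 52%, and positive correlation among influenza, ILI, ARI, fever and antiviral use would lower it further.
- *That the antiviral result fails in any family.* In a two-test Holm family with ARI at the printed values, the adjusted figures are 0.024 and 0.036, and both pass. No such family is defined in the SAP.
- *That ARI is simply a chance finding.* Its own counts give 0.0034, which only narrowly misses across 18 rows.
- *That AOM was added after the fact.* The protocol is not shown and may list it. AOM has p=0.358, drives neither claim, and only moves the count from 17 to 18.

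**Conclusion.** The concern holds in a limited form. The SAP applies an unadjusted 0.05 to 18 secondary comparisons without a multiplicity rule or exploratory label, and two infant results are called significant beside a primary chi-square comparison of 0.314.

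The antiviral claim is weak: 3 events, Fisher 0.067, and no survival across 10 or 18 rows. The status of ARI is undetermined. It fails both families at its printed p-value. From its counts it passes in one family and fails in the other, and the SAP fixes neither the family nor a correct p-value. The false-positive figure of about 60% is an illustration under independence, lower in practice. The recomputations assume that the printed counts and denominators are right.

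This changes how two secondary results may be described. It does not affect the primary chi-square result and does not show that the infant differences are absent.

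**What to change.** 1. In SAP, Statistical analysis, restrict the 0.05 significance rule to the primary outcome and state that secondary p-values are nominal, without multiplicity control.
2. Report every secondary row in Tables 2 and 3 with a risk ratio and 95% CI. Four rows have no events in the vaccinated group (maternal hospitalization; infant pneumonia, hospitalization and antivirals). Their risk ratio is 0 and the usual log-scale interval is undefined, so name an exact or score method for them.
3. In Results, Estimation of IVE in infants, reword the sentence on ARI and antivirals as a description of estimates and nominal p-values, without the claim of significance. Correct the ARI p-value or counts first, so that the two agree.
4. Reconcile AOM with the outcome list, or mark it in Table 3 as not on that list.

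Holm across all 18 rows is an alternative. However, the document already contains the results, so any family chosen now is chosen with the p-values in view, and that choice decides the recomputed ARI result. Nominal reporting avoids this.

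The cost is wording and a recalculation from counts already printed; no new data are needed. The downside is that two secondary claims become descriptive.
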